- s. When the Vital Status is determined, the subject should be asked if they have undergone a heart and/or liver transplant or implantation of cardiac mechanical assist device. If a subject indicates that they have had a transplant and they are still enrolled in the study, they should be removed from the study.
- In the event of early study discontinuation, the site staff will follow-up on the subject's vital status/transplant status 60 months after randomization/assignment date.
- u. Only countries listed in Appendix 5 may screen/enroll subjects in Cohort B. Upon availability of Day -30 disease confirmation results, subjects in Cohort B may return to the study site for Day 0 visit procedures.
- v. Cohort A: On Day 0, subjects in Cohort A will be blindly assigned to tafamidis meglumine 20 mg or 80 mg.
 Cohort B: On Day 0, subjects in Cohort B will be assigned to open label tafamidis 61 mg (or tafamidis meglumine 80 mg if unavailable).
- w. Cohort B only: Collect a genomic banked biospecimen. If missed, collect at the next available time point when biospecimens are being collected in conjunction with a subject visit.
- x. Cardiac biomarkers NT-proBNP and Troponin I sample collection effective after Protocol Amendment 4. Study subjects enrolled prior to Protocol Amendment 4 are required to sign an updated informed consent prior to providing blood sample for cardiac biomarker assessment.
- y. See Appendix 7 for Additional sample and banked biospecimen collection for newly enrolling subjects in specific countries. These samples will be used to support identification and characterization of serum, plasma, or urinary biomarkers of transthyretin amyloidosis. This collection introduced in Protocol Amendment 5 is relevant only to subjects participating in countries listed in Appendix 6.

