Subjects may be on a transplant list at the time of randomization/enrollment in the study. However, if a subject chooses to accept a donor organ transplant during the study or undergoes implantation of a cardiac mechanical assist device, they will stop taking blinded study medication and be discontinued from study participation prior to the transplant operation. Vital status/transplant status for the subject will be established through 60 months following the Screening visit. Subjects who discontinue from the study due to transplantation or implantation of a cardiac mechanical assist device will be handled in the statistical analysis as described in Section 9.2.1.

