9.3.1. Mortality (All-cause)

For Cohort A, time to all-cause mortality will be calculated from the first dose of the randomized treatment (Study B3461028). Treated subjects from the parent study B3461028 who discontinue prior to the start of this study will also be included in this analysis.

All-cause mortality will be analyzed using SAS Proc Lifetest; p-values will be from the log-rank test. Kaplan-Meier survival curves for each treatment group along with median survival times (if applicable) will be presented.

All-cause mortality will also be analyzed using Cox proportional hazards model with treatment and TTR genotype (variant and wild-type) as factors.

Subjects who discontinue for transplantation (ie, heart transplantation and combined heart and liver transplantation) or for implantation of a cardiac mechanical assist device, will be handled in the same manner as death. Data from subjects who drop out for a liver-only transplantation will be handled in the same manner as the data from all other censored subjects.

For Cohort B, time to all-cause mortality will be calculated from the first dose of treatment. The Kaplan Meier survival curve along with median survival time (if applicable) will be presented.

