# **3. ENDPOINTS AND BASELINE VARIABLES: DEFINITIONS AND CONVENTIONS**

# 3.1. Primary Endpoint(s)

Safety as measured by:

- All-cause mortality.
- Incidence of treatment-emergent adverse events.

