# 6. ANALYSES AND SUMMARIES

# 6.1. Primary Endpoint(s)

#### 6.1.1. All-cause Mortality

For Cohort A subjects, time to all-cause mortality will be calculated from Day 1 of the Study B3461028 based on the "Combined Mortality Analysis Set" as defined in Section 4.4. All-cause mortality will be analyzed using SAS Proc Lifetest; p-values will be from the log-rank test. Kaplan-Meier survival curves for each treatment group along with median survival times (if applicable) will be presented comparing tafamidis/tafamidis group with placebo/tafamidis group.

All-cause mortality will also be analyzed using Cox proportional hazards model with treatment, NYHA baseline classification, and TTR genotype (variant and wild-type) as factors. Subjects who discontinue for transplantation (ie, heart transplantation and combined heart and liver transplantation) or for implantation of a cardiac mechanical assist device, will be handled in the same manner as death. Data from subjects who drop out for a liver-only transplantation will be handled in the same manner as the data from all other censored subjects.

To examine the potential effect of including heart transplantation or cardiac mechanical assist device as "deaths" in the all-cause mortality analysis, a sensitivity analysis will be performed treating all transplantation or cardiac mechanical assist device in the same manner as any other censored observation.

For Cohort B, since subjects in this Cohort will all be administered the same dose, only overall descriptive statistics will be provided. Kaplan-Meier survival curve along with median survival time (if applicable) will be presented.

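### No planned analysis of the all-cause mortality endpoint estimates death from any cause regardless of heart transplant or assist device, although vital status is followed to 60 months in B3461045 enrollees who discontinue.

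*SAP*

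**What the plan says.** SAP 3.1 lists "All-cause mortality" as one of two primary safety endpoints, as does protocol 2.2.

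- **Main analysis.** In SAP 6.1.1, subjects who stop for a heart or combined heart-liver transplant, or for "implantation of a cardiac mechanical assist device, will be handled in the same manner as death". Protocol 9.3.1 has the same rule. Data after a "liver-only transplantation will be handled in the same manner as the data from all other censored subjects".
- **Only alternative.** SAP 6.1.1 adds one sensitivity analysis, "treating all transplantation or cardiac mechanical assist device in the same manner as any other censored observation".
- **Data used.** SAP 4.4 builds the Cohort A mortality set from the parent study's ITT set, with extension mortality data running through participation in B3461045. Protocol 6.4.1 ends participation before the transplant operation.
- **Data collected.** For recipients, protocol 6.4.1 says: "Vital status/transplant status for the subject will be established through 60 months following the Screening visit". After any early discontinuation, note t of the Schedule of Activities says that "the site staff will follow-up on the subject's vital status/transplant status 60 months after randomization/assignment date".

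**The concern.** The endpoint is named for death, but the main analysis estimates time to the first of death, heart transplant or assist device. Someone alive years after a transplant enters the Kaplan-Meier curve and the median as a death. The sensitivity analysis removes that problem but, on the natural reading, stops the clock at the transplant or device, so a subject who dies a month after implantation is not a death there. It also relies on censoring being unrelated to later risk, which cannot be taken for granted when the reason for censoring is a transplant or device.

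At stake is the absolute survival estimate. The study exists to supply long-term safety data, and Cohort B has no comparator, so its curve will be read as a death rate. Cardiovascular mortality is affected too: protocol 9.2.1 applies the same rule, and SAP 6.2.1 analyses it in the same way as all-cause mortality.

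**Working it through.** The plan states no sample size, event count or transplant count for this endpoint, so there is no planned figure to reproduce.

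**1. How each course of events is classified.** The SAP does not define the censoring date. Censoring at the event is the natural reading, supported by SAP 4.4.

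| Course | Main analysis | Sensitivity analysis | Actual death |
|---|---|---|---|
| Dies, no transplant or device | event | event | event |
| Heart or heart-liver transplant or device, still alive | event | censored | alive, still followed |
| Same, then dies | event, dated at the transplant or device | censored, death not counted | event at death |
| Liver-only transplant, then dies | censored | censored | event at death |

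Neither planned column matches the last one.

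**2. Who has later vital status.** Protocol 6.4.1 and note t cover subjects enrolled in B3461045. A subject who received a transplant or device during B3461028 is in the Combined Mortality Analysis Set but could not enter the extension (protocol 4.2.1, exclusion 3). These documents do not describe later follow-up for such subjects.

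**3. Possible counts.** The 1% to 5% share of recipients is an assumption.

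- Parent study, 441 subjects: 441 × 0.01 = 4.4 and 441 × 0.05 = 22.
- Against an assumed 220 deaths (about half of 441): 4.4 / 220 = 2% and 22 / 220 = 10% extra events. This is an upper bound, because some recipients would die during follow-up anyway.
- Cohort B, assumed 1500 subjects: 15 to 75 people, if the rule applies there.

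**4. Illustrative simulation; every rate is assumed.** Inputs: one million subjects per group; death rates of 0.20 and 0.14 per year (control, treated); a shared gamma frailty with variance 0.5 acting on both death and transplant or device; 30 + 60 = 90 months (7.5 years) of follow-up; and a death hazard after the event of 0.3, 0.6 or 1.0 times the hazard without it. The result is the ratio of events per person-year, treated over control.

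| Transplant/device rate per year | Recipients per 441 | Main rule | Censored | Actual death |
|---|---|---|---|---|
| Equal, 0.2% to 1% | 3 to 16 | 0.740 to 0.753 | 0.737 to 0.738 | 0.736 to 0.739 |
| 2:1 either way, 0.5% to 2% | 12 to 24 | 0.720 to 0.794 | 0.729 to 0.741 | 0.717 to 0.752 |

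- Largest gap between main rule and actual death: 0.753 − 0.737 = 0.016 with equal rates; 0.793 − 0.717 = 0.076 with 2:1 rates.
- Largest gap between censored and actual death: 0.729 − 0.717 = 0.012.
- Absolute effect: at 7.5 years the main curve lies below true survival by exactly the share of subjects who are recipients and still alive. In the simulation that share was 0.3% to 3.1% of a group with equal rates and 0.7% to 6.0% with 2:1 rates.

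**The case against.** The convention is open and deliberate. It stands in both documents, and the SAP added the sensitivity analysis expressly to test its effect. The study is primarily descriptive, and SAE incidence (which includes fatal events) and disposition are summarised separately. On this view the point asks only for a third handling of the same event. That much is fair and limits the severity, but those tables do not supply an estimate of death past transplant or device.

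Four stronger readings are tempting, and the documents do not support them:

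- **That neither analysis measures death.** Every event in the sensitivity analysis is a real death; what it lacks is deaths after the transplant or device.
- **That true death or last-alive dates exist for every recipient.** Recipients during B3461028 fall outside protocol 6.4.1, and registry searches depend on local law (protocol 6.4).
- **That censoring removes the sickest subjects and so understates deaths.** The documents say nothing about recipients' prognosis relative to others, so the direction of any bias is open.
- **That the group comparison is seriously distorted.** With the assumed rates, the effect is small unless transplant or device use differs between groups, and even then the planned censored analysis stays close to the actual-death ratio.

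For Cohort B, SAP 6.1.1 restates neither the transplant rule nor the sensitivity analysis. The rule in protocol 9.3.1 is not limited to one cohort, so its application there is an inference.

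**Conclusion.** The point holds as a mismatch between the endpoint's name and what is estimated, together with vital-status data that no planned analysis clearly uses. It rests on two readings: that censoring falls at the transplant or device, and that the protocol's rule reaches Cohort B. The real size cannot be known without transplant and device counts by group. On the assumed rates, the main analysis shifts the rate ratio by under 0.02 when use is equal and by up to about 0.08 at 2:1, while the censored version stays within about 0.012. No reversal of the Cohort A comparison is claimed. The practical consequence is for labelling and absolute survival, which makes this a worthwhile, inexpensive improvement and not a fundamental flaw.

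**What to change.** In SAP 6.1.1:

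1. Label the main analysis *death, heart transplant or assist device*, and keep it.
2. Add an analysis of actual deaths that follows recipients past the event to death or last known alive date. Use the 60-month vital-status data for B3461045 enrollees, and last known alive dates for subjects who received a transplant or device during B3461028.
3. Tabulate deaths, transplants and devices by group.
4. State that the same handling applies to Cohort B, and give the censoring date for each analysis.

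The cost is about one SAP paragraph plus a table and a figure per cohort, with no new data collection. Deaths after transplant partly reflect post-transplant care, so the composite should stay alongside the actual-death analysis and not be replaced by it.

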# 6.2. Other Endpoint(s)

As a general rule, data from endpoints that are collected at "Month 3" either in France or Germany as part of the country-specific protocol amendment will be included in study listings and will be summarized descriptively at that time point but will not be included in any inferential analyses. Data at Month 3 from one or two countries will be limited and could lead to convergence issues for the models used in the inferential analyses.

# 6.2.1. Cardiovascular-related Mortality

For both Cohort A and B, cardiovascular-related mortality will be analyzed separately similar to all-cause mortality detailed in Section 6.1.1. Cardiovascular relatedness will be based on an evaluation and clinical judgment of the MedDRA preferred terms.

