9.2. Analysis of Other Endpoints

9.2.1. Mortality (Cardiovascular-related)

For Cohort A, time to cardiovascular-related mortality will be calculated from the first dose of the randomized treatment (Study B3461028). Kaplan-Meier survival curves for each treatment group along with median survival times (if applicable) will be presented.

Subjects who discontinue for transplantation (ie, heart transplantation and combined heart and liver transplantation) or for implantation of a cardiac mechanical assist device, will be handled in the same manner as death. Data from subjects who drop out for a liver-only transplantation will be handled in the same manner as the data from all other censored subjects.

For Cohort B, time to cardiovascular related mortality will be calculated from the first dose of treatment. The Kaplan Meier survival curve along with median survival time (if applicable) will be presented.

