#### **Appendix 2. STATISTICAL METHODOLOGY DETAILS**

Sample SAS code for time to event analysis is given below.

PROC LIFETEST DATA=xxx PLOTS=(s) graphics; TIME dur \*status(0); STRATA trt; RUN;

PROC PHREG DATA=xxx; MODEL dur\*status(0)=trt genotype NYHAbase/ ties=EXACT; RUN;

Sample SAS code to fit the mixed model repeated measures is given below. The response variable Y is the change from baseline at the study visits.

PROC MIXED DATA=xxx METHOD=REML EMPIRICAL; CLASS pid center trt visit genotype; MODEL y= ybase trt visit genotype trt \*visit; RANDOM int/SUBJECT=center; REPEATED visit /SUBJECT= pid (center) r type=UN; RUN;

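### Cardiovascular mortality is displayed over time only by Kaplan-Meier; if non-cardiovascular deaths are censored, as the sample code implies, 1−KM read as absolute risk overstates cumulative incidence

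*SAP*

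**What the plan says.** SAP 6.2.1 defines the CV mortality analysis by reference: "cardiovascular-related mortality will be analyzed separately similar to all-cause mortality detailed in Section 6.1.1". For Cohort A, the section it points to specifies the test ("All-cause mortality will be analyzed using SAS Proc Lifetest; p-values will be from the log-rank test"), KM curves with medians where applicable, and a Cox model. For Cohort B it specifies overall descriptive statistics and adds that a "Kaplan-Meier survival curve along with median survival time (if applicable) will be presented".

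Protocol 9.2.1 names only the display. For Cohort A, "Kaplan-Meier survival curves for each treatment group along with median survival times (if applicable) will be presented". The Cohort B rule begins "For Cohort B, time to cardiovascular related mortality will be calculated from the first dose of treatment" and again ends in a KM curve and, if applicable, a median.

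Both documents count heart transplant, combined heart-liver transplant and an assist device as deaths, and censor liver-only transplant. Neither says what happens to a subject who dies of a non-CV cause.

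SAP Appendix 2 introduces its code with "Sample SAS code for time to event analysis is given below". The LIFETEST step contains "status(0); STRATA trt; RUN", and the PHREG step uses the same two-state status. There is no third state and no event code. Neither document mentions competing risks or a cumulative incidence function.

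**The concern.** A method written for all-cause mortality is carried over to a cause-specific endpoint. In the all-cause analysis no death can pre-empt the event. In the CV analysis a non-CV death does.

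With a single two-state status, a non-CV death must be either an event or censored. Calling it an event would simply reproduce the all-cause analysis, so censoring is what a programmer would most naturally do. The KM curve then treats a subject who died of, say, cancer as someone who could still have a CV death later. It describes CV risk net of non-CV death, not the proportion of subjects who actually have a CV event.

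At stake is the absolute risk that a reader takes from a long-term safety study. KM is the only time-to-event display of CV mortality planned, and the excess grows with cumulative mortality.

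**Working it through.** The documents state no mortality rate, CV share or event count for this endpoint, and protocol 9.1 has no sample size calculation, so there is no planned figure to reproduce. The size has to be shown over a range.

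**Inputs**
- F: cumulative all-cause events, counting heart transplant and assist device as the plan does. Assumed 20% to 70%.
- f: share of those events that count as CV, taken as constant over time. Assumed 0.9, 0.75 and 0.6.

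**Formulas.** Let H be the all-cause cumulative hazard, so 1−F = exp(−H). With a constant share, the CV cumulative hazard is fH. No constant hazard is needed.
- Cumulative incidence of CV events: CIF = f × F.
- KM with non-CV deaths censored estimates exp(−fH), so 1−KM = 1 − (1−F)^f.

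**Example, F = 0.5 and f = 0.75.** CIF = 0.75 × 0.5 = 37.5%. 1−KM = 1 − 0.5^0.75 = 40.5%. The gap is 3.0 points.

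**Gap (1−KM minus CIF), percentage points**

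| All-cause F | f = 0.9 | f = 0.75 | f = 0.6 |
|---|---|---|---|
| 20% | 0.2 | 0.4 | 0.5 |
| 30% | 0.5 | 1.0 | 1.3 |
| 50% | 1.4 | 3.0 | 4.0 |
| 70% | 3.2 | 7.0 | 9.4 |

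**Simulation check** (exponential times, staggered censoring, 300 runs each; mean estimates):
- n = 441, 90 months, F = 0.6, f = 0.8: 1−KM 52.0%, Aalen-Johansen 48.1% (true CIF 0.8 × 0.6 = 48.0%).
- n = 441, 90 months, F = 0.5, f = 0.7: 38.4% against 34.9% (true 35.0%).
- n = 2000, 60 months, F = 0.4, f = 0.8: 33.5% against 32.0% (true 32.0%).

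Aalen-Johansen recovers the true incidence and 1−KM does not.

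**Follow-up.** Cohort A is timed from the parent study, so the ceiling is 30 + 60 = 90 months. Cohort B has a ceiling of 60 months. Under protocol section 3, exit at commercial access applies to both cohorts, and Appendix 4.1 adds a conditional 24-month limit in France and Germany. Data near either ceiling may therefore be sparse.

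**The case against.** The strongest reply is that nothing planned is wrong as a cause-specific analysis. Censoring other deaths is the standard route to a cause-specific log-rank test and Cox model, and the documents plan survival curves, not 1−KM or event probabilities at fixed months. The overstatement needs a reader to make that conversion. All of this stands, which is why the point is confined to the display. A reader might infer that the Cohort A p-value or hazard ratio is biased; the documents do not support that.

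Censoring of non-CV deaths is also inferred from code labelled as a sample. That stands too. The plan does not prescribe the censoring; it leaves the coding unstated, and censoring is the natural reading.

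KM is not the only source of CV death frequency. Cohort B gets overall descriptive statistics, which could include counts and percentages, and serious adverse events are tabulated. This limits the claim to time-to-event displays. Crude percentages under unequal follow-up do not give risk at a stated month.

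The gap may also be small against sampling error. For 40.5% in all 441 parent-study subjects, pooled and uncensored, the 95% half-width is 1.96 × √(0.405 × 0.595 / 441) = 4.6 points, more than the 3.0-point gap in the example. That is fair, but the gap is systematic and removable at almost no cost.

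Two further inferences should be resisted:
- A reader might infer that the planned medians will mislead. They are reported only if applicable, and a KM median requires F above 1 − 0.5^(1/f), which is 53.7%, 60.3% and 68.5% for the three shares. Nothing in the documents shows mortality reaching those levels.
- A reader might infer that deaths of unknown cause add a material error. SAP 6.2.1 already assigns classification: "Cardiovascular relatedness will be based on an evaluation and clinical judgment of the MedDRA preferred terms". SAP 4.4 takes Cohort A's extension mortality data through study participation, and no document gives a share of undetermined causes.

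**Conclusion.** The point holds in a limited form. If non-CV deaths are censored, the KM curve is net of non-CV death, and 1−KM read as absolute risk is too high whenever the CV share is below 1. For CV shares of 0.9 to 0.6, the excess is about 0.5 to 1.3 points at 30% all-cause mortality and 1.4 to 4.0 points at 50%. It is larger only if mortality is higher. These sizes rest on assumed mortality, an assumed share and constancy of that share over time; the documents fix none of them.

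The effect stops at the absolute-risk display. The log-rank and Cox results are valid for the cause-specific hazard, and the all-cause primary endpoint has no competing death. CV mortality is listed among the Other endpoints, and no decision rule rests on it. The change is worth making because a better display is available from data already collected.

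**What to change.** In SAP 6.2.1 and Appendix 2:

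1. Code status as 0 = censored (including liver-only transplant); 1 = CV death, heart or heart-liver transplant, or assist device, as the plan already counts them; 2 = non-CV death.
2. Add Aalen-Johansen cumulative incidence of status 1 with 95% confidence intervals at fixed months, by treatment group for Cohort A and overall for Cohort B (PROC LIFETEST, `TIME dur*status(0) / EVENTCODE=1`). Make this the absolute-risk display.
3. For Cohort A, keep the log-rank test in a separate LIFETEST run with `status(0,2)`, because the EVENTCODE option gives Gray's test instead. Keep the Cox model with `status(0,2)`. Label both as cause-specific.
4. Label any KM curve or median that is kept as cause-specific, net of non-CV death.
5. If the transplant/device sensitivity analysis of SAP 6.1.1 is carried over to CV mortality, those events become 0.

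A one-line convention for deaths of undetermined cause is optional.

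The cost is one recode, one extra LIFETEST run per cohort and a few sentences in the SAP. No new data are needed. SAP section 2 calls for a protocol amendment only for major changes to the primary endpoint or its analysis, so none is required here.
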